7.0 Inclusion and Exclusion Criteria*

3.1 Eligibility Criteria:

Inclusion Criteria

- 1) Must be a parent aged 18+ (primary caregiver) of 2-6-year-old child with PFD
- 2) Child must be receiving outpatient PFD treatment at CMH
- 3) The parent must have a clinically significant elevation on at least one measure of parent MH (using established clinical cutoffs). Parents will be included regardless of whether the child has a new diagnosis or established diagnoses

Exclusion Criteria

- 1) Parent has significant cognitive impairments
- 2) Parent does not speak English
- Parent unable to obtain high speed internet at home

3.2 Equitable Selection: We are excluding non-English speaking participants because we are providing a behavioral intervention and do not have a translated version of the intervention available. In the future, we hope to translate this

intervention for non-English speaking patients but are unable to do this for the present study.

3.3 Vulnerable Populations: *Check any vulnerable populations that are being targeted for enrollment into the study: (Members of the following populations may not be included as participants in the research unless selected here.)*

 Children/Minors (under 7 years of age)	 CM Employees
 Children/Minors (7-17 years of age)	 CM Students/Residents/ Fellows
 Neonates (infants less than 30 days old)	 Economically or Educationally Disadvantaged Persons
 Neonates of Uncertain Viability (infants less than 30 days old)	 Prisoners
 Non-Viable Neonates (infants less than 30 days old)	
 Wards of the State	
 Fetuses	
 Pregnant Women	
 Adults with impaired decision-making capacity	

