8.0 Local Number of Participants

4.1

	Total consented (before meeting inclusion criteria)	Group 1 (Active treatment)	Group 2 (Control)	Total (meet criteria and randomized)
Enrollment Goal: Number of participants to be enrolled = the number of participants to be consented or to be screened for chart reviews.	80	20	10	30

Approximately 60% of subjects consented will not meet inclusion criteria after taking quantitative measures and so 80 subjects will need to be enrolled to meet 30 randomized subjects. If number of randomized subjects reaches 30 prior to 80 being enrolled, enrollment will cease.

SHORT TITLE:

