4.3 Pre-Screening prior to HIPAA Authorization

Will any of the identification methods checked above involve access to Protected Health Information (PHI) prior to obtaining HIPAA Authorization?

Yes

No

- *If yes, a "Partial Waiver of HIPAA Authorization" is required. Be sure to make this selection in the "HIPAA & Confidentiality" section below and complete [Addendum E: Waiver/Alteration of HIPAA Authorization](#)*

SHORT TITLE:

4.4 Recruitment of Potential Participants:

Parents will be screened at outpatient clinic visits to the CMH feeding clinic. Parents who agree to participate will then complete parent MH measures via REDCap on a tablet during the clinic visit. No PHI will be collected at this time. Potential subjects that meet inclusion criteria after completing the screening tool will be asked to participate in the study. At that time a ICF will be given to them and reviewed. All questions will be answered and adequate time will be given for a decision.

•

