21.0 Parental Permission and Adult Consent Process*

SHORT TITLE:

21.1 *For screening purposes, we will give the parents an information sheet explaining that we are asking them to complete questionnaires to see if they meet criteria to participate in the main part of the study and will answer any questions they have. We are requesting a waiver of the documentation of permission/consent for this. The parent completing the questionnaires will be considered implied consent.*

If parent meets inclusion/exclusion they will then be presented the consent document and consent discussion for the main part of the study will happen. If they do not meet inclusion/exclusion they will be thanked for their participation.

Waiver of Documentation of Permission/Consent

Permission/Consent form provided but signature will NOT be obtained (e.g. verbal consent)

Must complete Addendum A: Waiver of Documentation of Permission/Consent

Waiver of written documentation of permission of parent/LAR for pediatric participants

Study group(s) to which this method applies: This only applies to the screening section of the study

Waiver of written documentation of consent of adult participants

Study group(s) to which this method applies: This only applies to the screening section of the study

Waiver of written documentation of consent of participants turning 18

21.2 Permission/Consent/Consent at 18 Discussion: N/A – no pediatric subjects will be turning 18 during their enrollment in the study. Children enrolled in the study are under the age of 6 and therefore are not close to their 18th birthday. Individual data will be deidentified once the study is complete. We will not access patient data after the child is 18 years of age.

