24.0 Provisions to Protect the Privacy Interests of Participants*

24.1 Steps will be taken to protect the participant's privacy. The consent discussion will occur during a private meeting with the parent, and identifiable information will not be shared outside of the study team.

24.2 Efforts will be made to make the parents feel at ease with the research situation such as informing parents all procedures and questions are optional, and they can choose not to participate in any aspect of the research with no impact to their care in the RUBI clinic or at CM.

24.3 The research team will access the Interdisciplinary Feeding and Swallowing program schedule through the EMR and will screen patients' EMR data to determine if they are eligible for participation. This will be possible through a partial HIPAA waiver. Steps will be taken to ensure the participant's confidentiality is protected, and data will be stored in a secure drive that only study personnel have access.

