28.0 Statistical Analysis*

10.1 Data will be analyzed using SPSS. We will conduct descriptive statistics to evaluate the research endpoints of this study. We will

SHORT TITLE:

conduct correlations between demographic factors and endpoints to evaluate relationships that may influence these endpoints.

10.2 Quantitative Feasibility Analyses. Descriptive statistics (frequency counts, %s) will determine recruitment, retention, assessment, and intervention delivery success and will be compared to identified benchmarks of success (recruitment rate above 60%, and retention, assessment completion, and intervention completion rate above 80%). Factors that may impact success will be evaluated in relation to these outcomes using t- and chi-squared tests.

10.3 Qualitative Feasibility Analyses. Parent free text responses to feasibility questions will be imported into NVivo 12 software for coding. A coding tree will be developed a priori and periodically revised to include relevant inductive codes as emergent themes arise. Qualitative responses will then be double coded by PI and a graduate research assistant. Interrater reliability will be coded, with the goal of achieving 80% interrater reliability. PI mentor will provide direct supervision for data collection and analysis.

10.4 Proof of concept analyses. We use the Reliable Change Index (RCI; success defined as $RCI > 1.96$) to determine if there is a reliable signal of change for participants who are in the PACT (active treatment) group from baseline to post-treatment and follow-up. The RCI is a psychometric criterion used to evaluate whether change is significant at the level of the individual. An RCI will be calculated for each participant in the PACT (active treatment) group, using the following formula: $RCI = \text{observed difference score between measurements} / \text{standard error of measurement of the difference}$. We will assess proof of concept for change in parent stress, parent anxiety, and parent behavior at meals (measured by the DINE).

10.5 Given the feasibility and proof-of-concept nature of this study, we are interested in seeing if these study procedures are feasible and if there are meaningful improvements (e.g., several points of improvement on rating scales) rather than statistical significance. The sample size was therefore selected to ensure that a large enough group of participants can be evaluated to be reflective of a heterogeneous group of parents.

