10.6 Recruitment rate is the indicator of recruitment feasibility (# consented/total # eligible per week). We will track factors that may impact recruitment from both those who do and do not consent to participate (baseline characteristics, contact methods). Retention: The % of parents who are retained through the final measurement will be the indicator of retention success. Assessment: % missing data will be the indicator of assessment success. We will track factors that may impact assessment success (measure factors, baseline characteristics). Intervention delivery:

SHORT TITLE:

session completion rate will be the indicator of success. We will monitor factors that may impact intervention delivery (baseline characteristics, scheduling procedures).

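### As most naturally read, the recruitment rate compared with 60% covers only the second consent step; refusals of the mental health screen fall outside it and no count of parents approached is specified

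*Combined protocol and SAP*

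**What the plan says.** - **Definition.** Section 28.0, item 10.6: "Recruitment rate is the indicator of recruitment feasibility (# consented/total # eligible per week". Items 10.2 and 10.6 do not define either term further.
- **Benchmark.** Section 28.0, item 10.2 compares the rate with a threshold of 60%, one of four feasibility thresholds. Sections 2.2 and 4.0 repeat it.
- **Eligibility.** Section 7.0, inclusion criterion 3: "The parent must have a clinically significant elevation on at least one measure of parent MH (using established clinical cutoffs".
- **Who is screened.** Section 9.0, item 4.4: "Parents who agree to participate will then complete parent MH measures via REDCap on a tablet during the clinic visit".
- **Who is offered the main consent.** The same item: "Potential subjects that meet inclusion criteria after completing the screening tool will be asked to participate in the study". Section 21.1 gives the same order.
- **A second use of the consent term.** The table in Section 8.0 heads its column of 80 parents "Total consented (before meeting inclusion criteria", and Section 21.1 adds: "The parent completing the questionnaires will be considered implied consent".
- **A second use of the eligibility term.** Section 24.3 begins "The research team will access the Interdisciplinary Feeding and Swallowing program schedule through the EMR" and goes on to say that record data will be used to establish eligibility. Addendum E describes this step as finding people who nominally meet the criteria.

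**The concern.** Recruitment has two points at which a parent can say no: when asked to complete mental health questionnaires during the child's feeding clinic visit, and when offered the consent form for the trial. Only the second is visible to a ratio whose denominator requires a screening score. A parent who says no at the first point has no known status on criterion 3 and cannot be counted as eligible in the full sense.

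Feasibility is a primary aim (Section 1.0), and Section 3.0 presents this pilot as the step before an efficacy study. Planning that study requires knowing how many parents must be approached for each one randomized. A rate confined to screen-positive parents cannot supply that number, and it can look favourable at any level of screen refusal. Because the two terms have looser uses elsewhere in the protocol, an analyst could also compute a quite different ratio from the same data and reach the opposite conclusion against 60%.

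**Working it through.** **Inputs**
- Parents screened: 80; share not meeting criteria: about 60%; randomized: 30 (Section 8.0).
- Benchmark: above 60% (Section 28.0, item 10.2).
- *a* = share of approached parents who complete the screen. The documents give no figure; 90%, 70% and 50% are assumed below.
- *b* = share of screened parents meeting all criteria who sign the main consent.

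**Step 1. Reproduce the plan's figure.** Screen-positive parents = 80 × (1 − 0.60) = 32, against 30 to be randomized. The gap of 2 is consistent with an approximate 60%, since 1 − 30/80 = 62.5%.

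**Step 2. The rate on the natural reading.** Treating the 30 randomized as the signed consents, *b* = 30/32 = 93.75%, or about 94%. The quantity *a* does not appear. If *a* = 50%, then 80/0.50 = 160 parents are approached and 80 refuse the screen, and the reported rate is still 94%.

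**Step 3. The other pairings of terms.**

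| Numerator | Denominator | Result on the plan's figures |
|---|---|---|
| Signed main consent | Screen-positive | 30/32 = 94%, above 60% |
| Signed main consent | Eligible on chart data (24.3) | at most 30/80 = 37.5%, below 60% |
| Screened (8.0, 21.1) | Eligible on chart data (24.3) | equals *a*; not given |

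The second row is a maximum because at least 80 such parents must be approached for 80 to be screened. It counts screen failures as well as refusals, so it is not a measure of refusal alone.

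**Step 4. Illustration with refusals counted.** If refusers have elevated scores as often as screened parents, overall uptake among eligible parents is *a* × *b*. With *b* = 0.9375:

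| Assumed *a* | Approached (80/*a*) | Refuse screen | Rate as defined | *a* × *b* |
|---|---|---|---|---|
| 90% | 89 | 9 | 94% | 0.90 × 0.9375 = 84% |
| 70% | 114 | 34 | 94% | 0.70 × 0.9375 = 66% |
| 50% | 160 | 80 | 94% | 0.50 × 0.9375 = 47% |

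For the product to exceed 60%, *a* must exceed 0.60/0.9375 = 64%. Even at *b* = 100%, *a* must exceed 60%.

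**Step 5. Is the first refusal captured elsewhere?** Section 2.2 lists surveys, the percentage meeting criteria and the number of contact attempts as recruitment factors. Section 4.0 places the qualitative surveys at the 3-month follow-up, which screen refusers never reach. Item 10.6 promises to track factors for consenting and non-consenting parents alike. None of these specifies a count of parents approached or of parents refusing the screen.

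**The case against.** The strongest reply is that the protocol does contain a wider meaning of each term. If eligibility is taken from the record review in Section 24.3, and consent is taken as completing the screen (Sections 8.0 and 21.1), the ratio becomes screened over chart-eligible, and refusals at first approach do count. A reader might infer that such refusals can never enter the rate; the documents do not support that. This reading is nevertheless the weaker one: chart data are not described as giving the parent's mental health score, Addendum E calls the chart match nominal, and the main consent follows the screen in both Section 9.0 and Section 21.1. It also leaves the ambiguity in place.

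Four further inferences should be resisted.

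- Dividing the 80 parents labelled as consented by the 32 screen-positive gives 250%. This shows inconsistent vocabulary only; it is not a rate that anyone would set against 60%.
- No passage makes 60% a go/no-go rule for the efficacy study. It defines feasibility success, descriptively.
- Nothing in the documents shows that many parents will refuse. Screening takes place at an existing visit, needs no signature and carries a $5 payment (Sections 9.0, 21.1 and 18.0), all of which may limit refusal.
- Consents over eligible parents is an ordinary measure of willingness to join a trial. Nothing shows that 60% was meant for *a* × *b*, so moving the benchmark to that product would change the sponsor's criterion.

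The tracking of factors in Section 2.2 and item 10.6 also shows that recruitment barriers are not ignored, although it does not put refusals into the rate. What stands against the plan is the undefined ratio and the missing count.

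**Conclusion.** The concern holds in a limited form. On the natural reading, the benchmarked rate describes only the second consent step, and it would be 94% on the plan's own figures whatever share of parents refuse the screen. Under the alternative use of eligibility in Section 24.3, the same figures give at most 37.5%. The plan does not say which applies.

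The size of any overstatement cannot be fixed from the documents. The illustrative 84%, 66% and 47% rest on three assumptions: the uptake values themselves, equal prevalence of elevated scores among refusers and screened parents (which this design cannot check), and the 30 randomized standing for the signed consents. The finding affects how the primary feasibility result can be interpreted and used for planning; it does not touch participant safety or the proof-of-concept analysis. It is a cheap improvement that is worth making.

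**What to change.** In Section 28.0, item 10.6, log and report cumulatively over the whole recruitment period:

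- (a) parents completing the mental health screen / parents approached who meet the chart-verifiable criteria (child aged 2 to 6 with PFD, in outpatient treatment at the centre);
- (b) parents signing the main consent / screened parents meeting all criteria;
- the overall yield a × b, with its equal-prevalence assumption stated, and the count at each stage.

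State which ratio the 60% benchmark applies to. If the sponsor keeps it on (b), say so, and do not conclude from (b) alone that recruitment is feasible. The cumulative rule also settles the weekly wording in item 10.6, which does not say how weeks are combined before comparison with 60%. In Section 8.0, label the 80 parents as screened rather than consented.

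The cost is protocol wording and a simple tally of approached and refusing parents, kept from the clinic schedule that the team already reviews. The downside for the sponsor is a less favourable overall recruitment figure printed beside the benchmarked rate.

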2.0 Objectives*

2.1 Purpose, specific aims or objectives: Primary Aim: Test the hypothesis that PACT will result in clinically meaningful reductions in Mental Health(MH) problems among parents of children with Pediatric Feed Disorder (PFD) and identify factors that impact the feasibility of intervention delivery. This pilot study will involve conducting recruitment procedures for 4 months (or until parent N=30). Participants will be parents of 2- to 6-year-old children with PFD in outpatient treatment for their PFD. Parents will be randomly assigned to PACT or an attention control condition (control). Secondary aim: Test the hypothesis that PACT-F will result in clinically meaningful improvements in parent use of positive behaviors at meals, as measured through an observation of a representative mealtime.

2.2 Hypothesis: We will test the hypothesis that PACT results in clinically meaningful change in parent stress and anxiety, and parent use of positive mealtime behaviors, using the Reliable Change Index (RCI; success defined as $RCI > 1.96$). We anticipate that these procedures will be feasible, with feasibility success defined as recruitment rate above 60%, and retention, assessment completion, and intervention completion rate above 80%. Mixed methods data collection will identify factors that impact 1) recruitment rate (qualitative surveys, % meeting inclusion criteria, # of contact attempts), 2) retention rates (qualitative surveys, baseline characteristics; treatment group), 3) assessment completion rate (qualitative surveys, measure type), and 4) treatment completion rate (qualitative surveys, scheduling, treatment location).

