4.0 Study Endpoints

Parents will complete the standard study battery at baseline, post-intervention, and 3-month follow-up.

Quantitative Measures. Feasibility success is defined as recruitment rate above 60%, and retention, assessment completion, and intervention completion rate above 80%.

SHORT TITLE: PACT Study

Demographics. Parents will provide information on their own and child's age, sex/gender, race/ethnicity, education, and socioeconomic status.

- Parent Mental Health (MH) Measures.
 - PHQ-9. A 9-item self-report measure of depressive symptoms. Scores of 10 or more indicate probable depression.
 - GAD-7. A 7-item self-report measure of anxious symptoms. Scores of 10 or more indicate probable anxiety.⁸⁷
 - IES-R. A 22-item self-report measure of posttraumatic stress symptoms. Scores of 33 or more indicate clinically significant posttraumatic stress.
 - PSS. A 10-item self-report measure of perceived stress. Scores of 14 or more indicate clinically significant stress.
 - AAQ-2. A 7-item self-report measure of psychological flexibility and experiential avoidance, which are targets of the behavioral treatment.
- Child Health.
 - PedsQL 4.0 (Generic). A 23-item parent-proxy measure of child quality of life, with versions specific to child age (2-4 years, 5-7 years) that each result in standardized total scores and domain-specific scores of physical functioning, emotional functioning, social functioning, and school functioning.
 - BPFAS. A 35-item parent-proxy report of child mealtime and feeding behavior.
- Qualitative Measures. Qualitative surveys will be completed by parents at the 3-month follow-up, focused on factors that impact feasibility. Feasibility of 1) recruitment procedures, 2) intervention procedures, and 3) measure completion.

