6.0 Study Intervention/Investigational Agent*

Active Treatment (PACT-F) and Control Interventions. Parents randomized to PACT-F will complete two 90-minute PACT-F sessions individually with a study interventionist, 2-weeks apart. Parents randomized to the control group will complete two 90-minute sessions individually with a study interventionist, 2-weeks apart (focused on nutrition education). The control intervention will be parallel

SHORT TITLE: PACT Study

to the PACT-F intervention, equal in the number of interactive components and duration of face-to-face time with health professionals (interventionists). Interventionists for both conditions will be individuals with at least master's-level training in mental health or a related field. Based on guidance from our parent consultants, we will deliver intervention sessions through Microsoft Teams to reduce barriers to participation (e.g., travel, childcare).

PACT-F. PACT-F is a 2-session intervention based on the Focused Acceptance and Commitment Therapy treatment literature^{14,30} and the two-session PACT approach utilized by Brown¹⁶ and Whittingham¹⁵ with parents of children with neurodevelopmental conditions. PACT-F content includes 1) education about parent MH problems among parents of children with PFD, 2) interactive learning of FACT skills, including cognitive defusion, mindfulness, and value-based decision making, and 3) education about the importance of positive parent-child interactions at mealtime and how to apply PACT-F skills to their mealtime interactions with their child with PFD. Each session lasts 90 minutes and will be conducted remotely via Microsoft Teams.

Control. The content of the control intervention covers a range of nutrition and healthy lifestyle topics including USDA's *MyPlate*. The control condition has equivalent face-to-face time with the interventionists.

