10.0 Procedures

[figure not shown]
Parents who meet inclusion criteria and sign consent will be randomized to either PACT-F or an attention control (control) condition using block randomization, such that an equal number of patients presenting for a new diagnosis and with an established diagnosis are randomized to each group. Participants will be blind to treatment condition (single blind study). See Figure 1 below for procedures. Intervention. Parents randomized to PACT-F will complete two 90-minute PACT-F sessions individually with a study interventionist, 2-weeks apart (see Table 2 for intervention content). Parents randomized to the control group will complete two 90-minute sessions individually with a study interventionist, 2-weeks apart (focused on nutrition education). The control intervention will be parallel to the PACT-F intervention in all ways, including interactive components and the face-to-face time with health professionals (interventionists). The control condition intervention has already been developed by [name] research team and covers a range of nutrition and healthy lifestyle topics including USDA's *MyPlate*. Interventionists for both conditions will be individuals with at least master's degree training in mental health or a related field. The interventions will take place remotely via telehealth. The team has expertise in remote delivery of therapy in both clinical and research environments. Both arms of the intervention will be manualized and interventionists in both arms will be trained using didactics and role playing with the PI. Intervention fidelity will be monitored by audio recording all sessions. The PI ([name]) will review video recordings each week and conduct weekly supervision.

Due to the nature of the study, the participants will be blinded to the group assignment during treatment. This is necessary as knowledge of whether they are in the treatment or control group may change behaviors of the participants. We will therefore not be able to give specific descriptions of the treatments in each group in the Informed consent form. Participants will be informed of their group assignment after they have completed the 3-month follow up and if they were in the control group be given the opportunity to participate in the treatment group. There is no difference in risk for either group.

Once the 3-month follow up is complete the subjects will be contacted and unblinded and control subjects will be offered the active treatment.

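### Does the undefined session completion rate make the 80% intervention-completion benchmark unreliable?

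*Combined protocol and SAP*

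**What the plan says.** Sections 2.2 and 4.0 and item 10.2 of Section 28.0 set the same benchmark. In Section 4.0 it reads "retention, assessment completion, and intervention completion rate above 80" per cent. Section 2.2 also uses a different label when it lists influencing factors: "treatment completion rate (qualitative surveys, scheduling, treatment location".

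Item 10.2 makes the comparison descriptive, using frequency counts and percentages: "intervention delivery success and will be compared to identified benchmarks of success". It then relates possible influencing factors to these outcomes by t- and chi-squared tests.

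Item 10.6 names an indicator for each benchmark. Recruitment has a numerator and a denominator. Retention has a unit: "The % of parents who are retained through the final measurement will be the indicator of retention success". For intervention delivery the text is only "session completion rate will be the indicator of success".

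Section 6.0 says "PACT-F is a 2-session intervention", and Section 10.0 repeats the schedule: "Parents randomized to PACT-F will complete two 90-minute PACT-F sessions individually with a study interventionist, 2-weeks apart". The control arm also has two sessions. Section 8.0 plans 30 randomized parents, 20 active and 10 control. Section 2.1 allows a smaller sample, because recruitment means "conducting recruitment procedures for 4 months (or until parent N=30").

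**The concern.** The benchmark is named for completion of the intervention, but its indicator is named for sessions. If the rate is sessions completed over sessions planned, a parent who stops after the first session counts as half complete. If it is parents who finish both sessions, that parent counts as zero. The two rates differ whenever anyone attends exactly one session, and near 80% they can give opposite answers.

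Feasibility belongs to the primary aim, so a result of met or not met should not rest on a unit chosen after the data are seen. The contrast with retention, which is stated per parent in the same item, makes the omission stand out.

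**Working it through.** The 80% threshold is a fixed benchmark with no derivation, so there is no figure in the plan to reproduce. The check is a count.

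**Inputs.** n = 30 randomized parents, 20 and 10 by arm (Section 8.0). Two sessions per parent in both arms (Sections 6.0 and 10.0). Success means strictly above 80% (Sections 2.2 and 4.0, item 10.2).

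**Notation.** b = parents attending both sessions, o = parents attending one only, S = 2b + o, with b + o ≤ n.

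**Per-session rule, all randomized.** S/60 > 0.80 needs S ≥ 49, since 48/60 is exactly 80%; 49/60 = 81.7%.

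**Per-parent rule, all randomized.** b/30 > 0.80 needs b ≥ 25, since 24/30 is exactly 80%; 25/30 = 83.3%.

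**Range of b at S = 49.** From o = 49 − 2b ≥ 0, b ≤ 24. From b + o = 49 − b ≤ 30, b ≥ 19. So 19 to 24 of 30 parents (63.3% to 80.0%) finished both.

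**Where the rules can disagree.** At S = 54, b can still be 24 (24 × 2 + 6 = 54). At S = 55, b ≥ 55 − 30 = 25. Disagreement is therefore confined to 49 to 54 sessions.

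| Set counted | Sessions needed | Parents needed | Parents finishing both when only the session rule is met |
|---|---|---|---|
| All 30 | 49/60 (81.7%) | 25/30 (83.3%) | 19 to 24 |
| PACT-F, 20 | 33/40 (82.5%) | 17/20 (85%) | 13 to 16 |
| Control, 10 | 17/20 (85%) | 9/10 (90%) | 7 or 8 |
| 24 parents (assumed shortfall) | 39/48 (81.3%) | 20/24 (83.3%) | 15 to 19 |

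**How many single-session parents it takes.** To reach S ≥ 49 with 24 finishing both, 1 of the other 6 must attend one session. With 23 it takes 3 of 7, with 22 it takes 5 of 8, with 21 it takes 7 of 9, with 20 it takes 9 of 10, and with 19 all 11. With 18 it cannot happen, because 36 + 12 = 48.

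**Direction.** On a common denominator S ≥ 2b, so S/(2n) ≥ b/n and the session rate is never the stricter one. With different denominators this fails. Suppose 5 of 30 never start, 21 attend both sessions and 4 attend one. Parents among starters: 21/25 = 84%, met. Sessions over all planned: (42 + 4)/60 = 46/60 = 76.7%, not met.

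**Overlap with retention.** In the 19-parent case, if the 11 who missed the second session also leave the study, retention is 19/30 = 63.3% and fails its own 80% benchmark.

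**The case for a change.** The case for a change is that item 10.6 is the only place that names this indicator and that it uses three words where recruitment is given a ratio. Disagreement does not need extreme attendance: with 24 parents finishing both, one single-session parent reverses the answer. As an illustration, assume all 30 attend the first session and each attends the second independently with probability 0.75; the chance of meeting the benchmark is then 0.949 per session and 0.203 per parent. Moreover, the planned tests relate baseline characteristics to delivery. Counting sessions would give two correlated observations per parent, which those tests do not allow for. One sentence would settle all this.

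What stands is that the denominator, the arm and the meaning of completion are not written down, and the counts are correct. The rest is weaker. The wording does name a unit, the session, and it appears under intervention delivery, where the share of planned sessions delivered is a usual thing to report. It overstates completion only if completion means both sessions, which the plan does not say. The argument from the tests works the other way too: baseline characteristics belong to parents, so the tests point to a parent-level outcome, and on that reading the discrepancy disappears. That is not conclusive, since scheduling factors could be examined per session. The attendance probabilities are assumed and have no source in the plan.

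Nor is there one obviously right definition to impose. Pooling the arms and using PACT-F alone are both defensible, since the primary aim centres on PACT, and they can differ: 17/20 + 7/10 = 24/30 misses the pooled threshold, while 16/20 + 9/10 = 25/30 meets it, although the PACT-F rate alone passes in the first case (85%) and not in the second (80%).

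**Conclusion.** No change to the plan is needed. The gap is one of definition in a descriptive rate. At the planned size the two natural readings can disagree only between 49 and 54 of 60 sessions, with 19 to 24 of 30 parents finishing both; the lower end requires every parent to attend the first session and exactly 11 to miss the second. These figures assume all 30 randomized parents as the denominator for both rates; with other denominators the direction can reverse.

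Either reading is acceptable if labelled when reported. The plan ties no decision rule to the result, so the effect is confined to how completion is described. The planned frequency counts, tabulated by arm as parents attending none, one or both sessions, let any reader compute either rate. The retention benchmark covers part of the adverse case, though not parents who skip the second session and still complete the final measurement. Writing the definition into item 10.6 would be harmless, but it would alter neither the data collected nor what can be concluded from them.
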